Despite lower TG levels and less visceral adiposity, we found that AA women with PCOS ages 20-34 years have significantly increased risk of MetS compared to White women⁶ indicating racial disparity in cardiometabolic risk factors (Table 2). Inclusion of AA women in studies examining metabolic outcomes in PCOS is therefore critical and we will stratify our randomization by race.

Table 2. Racial Disparity in MetS	N	Metaboli c Syndrom e	BMI≥3 0 kg/m2	TG≥ 150 mg/dL	HDL ≤ 50 mg/dL	BP≥ 130/85 mmHg	Glucos e≥ 100 mg/dL
PCOS White	2	22.6 %	51.7	24.6	35.6%	31.9%	4.9%
PCOS Black	6	40 %**	72.7	10.9	76.6%	45.5% *	18.8%
NHANES white	2	14.9%	66.1	15.5	39.9%	3.3%	9.0%
NHANES black	1	16.6%	75.4	9.9%	42.9%	10.6%*	8.3%

Effect of OCP on MetS

The OWL PCOS Study – We have recently completed an NIH funded study, OWL- PCOS at PENN and Hershey examining the effects of pretreatment with low dose OCP (20ug ethinyl estradiol) versus weight loss interventions for 16 weeks, on pregnancy rates in overweight/obese women with PCOS⁷. Surprisingly, the OCP arm showed a significant increase in MetS [OR=2.47; 95% CI 1.42, 4.27]; with no change in the intensive Lifestyle modification with pharmacotherapy arm [OR=1.18; 95% CI 0.63, 2.19)] or Combined arms [OR=0.72; 95% CI 0.44, 1.17]. The conversion rate to MetS was 28% in the OCP arm with significant increase in TG levels, and trend towards increase in BP and fasting glucose levels. Interestingly, we noted a significant decrease in VAT after treatment with OCP (Table 3) but an increase in glucose AUC. Our study suggests early onset metabolic dysfunction only in the OCP group, and this was attenuated in the Combined group with the addition of lifestyle modification associated with weight loss. We have previously shown that women with PCOS have a high risk for depressive disorders (OR 5.11 95% CI 1.26- 20.69; P<.03)⁸ and this risk persists over time⁹. In the OWL-PCOS study there was in fact an improvement in depressive symptoms and health related quality of life scores with OCP treatment⁷. These findings underscore the need for a clinical trial to comprehensively compare the effectiveness of therapeutic alternatives with specific focus on metabolic outcomes in addition to gynecological, dermatological and mood changes. Understanding the associated pathophysiological changes will add great value to this clinical trial.

Table 3. Effect of OCP on Visceral Adipose Tissue	Mean Change from Baseline (95% CI)	P- valu

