It is suspected that the combination of OCP+metformin may be an appropriate comparator to address gynecological, dermatologic and metabolic end points in PCOS. Only one clinical trial has included three arms namely OCP *vs* metformin *vs* OCP+metformin but included lean and obese women (n=65) with PCOS⁷⁰ showing improvement in body fat distribution in the OCP+metformin arm⁷¹.

This clinical trial examined traditional CV markers, lacked mechanistic data and most importantly was not powered to provide clear recommendations. Overall these limited data present a clinical conundrum and underscore the need to answer important clinical questions; do OCP increase the risk of MetS in overweight/obese women with PCOS, can metformin mitigate these effects and therefore will the combination of OCP+metformin offer the best outcomes for improving menstrual regularity, decreasing hyperandrogenism and improving CV risk?

Further complicating matters, PCOS treatment practice patterns vary depending on the physician (i.e. pediatrician, gynecologist or endocrinologist) treating adolescent and adult women with PCOS not seeking fertility. In physician surveys metformin was noted to be preferentially used by Australian and European endocrinologists^{72,73} while pediatricians and gynecologists practicing in the US frequently prescribed OCP as first line therapy⁷⁴. Besides

competing guidelines from several international medical Societies, ^{32,33,34,75} there are no formal recommendations for CV risk stratification prior to prescribing these medications1. Although the best therapeutic approach for MetS is lifestyle modification, such programs alone have high dropout rates necessitating pharmacotherapy to achieve and maintain weight loss⁷⁶. It is therefore critical to identify appropriate medical therapy whilst avoiding medications that might alter the risk of MetS in this young but high risk population. The overall goal of COMET-PCOS is to provide practitioners with evidence for the selection of the most appropriate treatment for overweight/obese women with PCOS by carefully defining the clustering of metabolic risks and benefits associated with three interventions - OCP, metformin or OCP+metformin.

Effects of OCP vs. metformin vs OCP + metformin on individual components of MetS

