In summary, evaluation of MetS risk modification associated with treatments such as OCP and/or metformin in a high risk PCOS population is urgently needed and will have a major impact on current clinical practice.

Implications for the COMET-PCOS Trial

This project brings together a multidisciplinary exceptionally well-qualified team with demonstrated expertise in reproductive endocrinology, cardiometabolic risk assessment and inflammation and clinical trials to study two major health issues namely, PCOS and MetS. Our study includes four highly innovative components:

First Due to lack of evidence there is currently no consensus regarding the medical management of overweight/ obese women with PCOS. OCP and metformin, though currently in use, have differing treatment outcomes and safety profiles, resulting in conflicting guidelines for use in PCOS. COMET-PCOS will be the first 3 arm clinical trial to be adequately powered to provide evidence for single agent versus combination therapies for medical management of PCOS. It will have significant impact on current clinical practice paradigms much like the impact of the PPCOS1 trial (Clomid versus metformin versus clomid+metformin)¹¹¹.

[figure not shown]
Second Based on our recent findings from OWL-PCOS we have included MetS as a composite endpoint to provide comprehensive assessment of early CVD risk in this young population.

Third We have included innovative mechanistic secondary aims and will apply novel concepts to the assessment of dyslipidemia, the commonest metabolic abnormality in PCOS. We will measure HDL-C function (cholesterol efflux capacity) and lipoprotein particle size and number using NMR spectroscopy to clearly define the atherogenic impact of the three therapeutic interventions.

Fourth Recognizing that there are racial disparities in metabolic components in PCOS, we will stratify the randomization in our primary aim by race. This will provide unique observations of potential importance.

Study Design

Overview

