Urine Pregnancy Test: A urine pregnancy test will be performed for all subjects at every visit. If a positive result is found, the subject will be informed by site staff of positive result and offered resources regarding prenatal care or alternative options. In the case of a positive pregnancy result, subjects will be withdrawn from the study. In the case of a subject becoming pregnant, the subject will have the choice to consent to allow the study team to track until outcome of the pregnancy.

Vital Signs and Biometrics: Vital signs and biometrics for this study include but are not limited to, measuring height and weight, blood pressure, pulse, waist and hip circumference. Vital signs and biometrics will be collected at every visit except height which will only be recorded at the screening visit. Blood pressure and pulse will be measured in sitting position at all visits after the subject has rested for at least five minutes. Three blood pressure measurements will be taken 5 minutes apart and then averaged.

Laboratory Evaluations: Blood will be collected at Screening, Randomization, week 16 and week 24 visits (early termination visit). Subjects will be required to be fasting prior to Screening, Randomization, week 16 and week 24 visit (nothing to eat or drink besides water for a minimum of 8 hours prior to blood draw). Subjects who have used hormonal contraception must wait at least 30 days prior to the collection of screening and fasting blood I tests. Screening blood tests that were completed within the last year can be substituted for laboratory tests collected at screening visit.

Transvaginal Ultrasound: Transvaginal ultrasound examinations will be performed at screening if indicated, randomization and 24 week visit (or early termination visit). The transvaginal ultrasound examinations will be performed according to the standard procedure for the center and include finding regarding the uterus, the endometrium and the ovaries. If a transvaginal probe is not tolerated, then transabdominal ultrasound may be used. The same procedures were used in the OWL-PCOS study and are well known by the centers.

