The primary outcome of the COMET-PCOS trial will be to assess a linear trend in prevalence of MetS after 6 months' treatment over the 3 arms assuming a 30% prevalence of MetS at baseline (derived from PENN data and OWL-PCOS). We anticipate a 15% subject drop-out over the course of the trial (in OWL-PCOS it was 8.1% over 16 weeks). Based on these assumptions, a sample size of 240 (80 per arm) will provide 80% statistical power to detect a linear trend in the prevalence of MetS over the 3 arms at the end of 6 months of 26% in the metformin arm, 40% in the OCP+metformin arm and 50% in the OCP arm using a two-sided test for linear trend with a significance level of 0.05.

Proportion with MetS at the End of the Trial in Metformin Arm	Proportion with MetS at the End of the Trial in OCP+Metformin Arm	Proportion with MetS at the End of the Trial in OCP Arm	Total Sample Size (0% Drop-out)	Total Sample Size (15% Drop-out)	Power (%)	Type I Error (α)
0.25	0.38	0.50	204	240	84	0.05
0.25	0.38	0.52	204	240	89	0.05
0.26	0.40	0.50	204	240	80	0.05
0.26	0.40	0.52	204	240	86	0.05
0.28	0.42	0.52	204	240	80	0.05

Table 10: Sample size scenarios based on varying assumptions

Statistical Analysis

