Primary analyses will invoke an intent-to-treat paradigm, wherein all randomized subjects are included according to their randomized treatment arm, regardless of actual treatment received, protocol violations, etc. Data will be summarized using descriptive statistics for continuous variables (mean, standard deviation, number of observations, and percentiles) and frequency statistics (frequencies and percentages) for categorical variables. The area under the curve (AUC) for glucose and insulin from the OGTT will be calculated using the trapezoidal rule. Univariate and bivariate distributions will be inspected in order to address any missing data, inconsistent responses, outliers, and data entry errors. The sample size estimates have taken into consideration a participant drop-out of 15%; however, every effort will be made during the studies to minimize any drop-out. If, however, study attrition appears to be an issue, we will use the observed data to determine if patients who completed the study differed from those who did not. To control for potential confounding factors for the association of the treatment effects with the metabolic syndrome, we have stratified the randomization by recruitment site, race, and the presence of metabolic syndrome at baseline. Although stratification may potentially yield unequal numbers between strata, within each individual stratum there will be approximately equal numbers and balance between treatment groups. All analyses will include these 3 randomization stratification factors as covariates in the statistical models. All hypothesis tests will be two-sided and all analyses will be performed using SAS software, version 9.4 (SAS Institute, Inc., Cary, NC), R software (open source), or Stata software, version 13 (StataCorp LP, College Station, TX).

For the primary outcome of the presence of the metabolic syndrome at the end of the 6-month trial, logistic regression will be used with independent variables that include terms for the treatment arm and the 3 randomization stratification factors as covariates, with a contrast constructed to test for linear trend over the three treatment arms.

A variety of secondary continuous outcomes will be collected during this longitudinal trial. These secondary outcomes include serum androgens, cholesterol efflux (HDL-C function) parameters, serum apolipoproteins, lipid particle size and number, anthropometric measures (BMI, adipokines, biomarkers of inflammation (e.g., hsCRP),

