measures of adipose tissue, abdominal adiposity, and quality of life measures (PCOSQ). For these continuous outcomes, linear mixed-effects models will be fit to assess differences between the treatment arms with respect to changes in these outcomes over time. The independent variables in the model will be treatment arm, time, the interaction of treatment and time, and the 3 randomization stratification factors as covariates. From the mixed-effects models, contrasts will be constructed to test the hypotheses of interest with respect to changes over time in the outcomes. Linear mixed-effects models are an extension of ordinary regression models that account for the between- and within-subject correlation inherent in longitudinal trials. Further, linear mixed-effects models do not drop patients with incomplete data and are easily extended to nonlinear mixed-effects models for ordinal data and count outcomes. Following our assessment of the initial fit of the models, we will add covariates to the models that correspond to other potential confounders (e.g., age) to assess their impact, if any, on the treatment effects. Residual diagnostics will be assessed to determine the appropriateness of the model fit and, if necessary, transformations of the response will be used to quantify the magnitude of the effects.

For any binary outcomes collected at each visit, analyses will be based on generalized estimating equations (GEE) with a logit link, an extension of logistic regression that accounts for correlated data within-subjects inherent in longitudinal trials, with independent variables that include terms for the treatment arm, time, the interaction of treatment and time, and the 3 randomization stratification factors as covariates. Following our assessment of the initial fit of the models, we will add covariates to the models that correspond to other potential confounders (e.g., age) to assess their impact, if any, on the treatment effects. The effect size will be quantified using the odds ratios (OR) and corresponding 95% CI.

Accrual

A total of 5 years will be required to complete the study after start up; 36-month enrollment period (based on 3 subjects per site/month x 2 sites), 1-month screening/randomization period, 6-month treatment period and time built in for data analysis and interpretation.

Data Collection, Monitoring and Adverse Experience Reporting

Records to be kept

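### The only MetS test planned and powered is a linear trend; the combination is never compared with either single agent, although the protocol claims adequate power for that comparison

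*Combined protocol and SAP*

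**What the plan says.** **Planned test.** The Statistical Analysis text, in the Synopsis and under Sample Size and Accruals, specifies logistic regression for MetS at the end of the trial, with treatment-arm terms and the three stratification factors, "with a contrast constructed to test for linear trend over the three treatment arms". The contrast coefficients are not written out. On adjustment it adds: "All analyses will include these 3 randomization stratification factors as covariates in the statistical models".

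**Power.** Sample Size and Power Calculations gives 80% power with 240 women for "26% in the metformin arm, 40% in the OCP+metformin arm and 50% in the OCP arm using a two-sided test for linear trend", at two-sided 0.05 and 15% drop-out. Table 10 varies the rates for the same trend test. No other power calculation appears.

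**Claims.** Implications for the COMET-PCOS Trial describes the study as "adequately powered to provide evidence for single agent versus combination therapies". The background section on the three regimens asks: "do OCP increase the risk of MetS in overweight/obese women with PCOS, can metformin mitigate these effects". The second half of that question is combination versus OCP. The Synopsis hypothesis expects the combination to lower MetS prevalence but names no comparator.

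**The concern.** A three-arm trend test answers whether prevalence rises along an assumed order of arms. It does not say where the middle arm lies. Here the middle arm is the combination, which is the arm that the background question and the power claim are about. If the trend is significant, readers will want to know whether adding metformin to OCP helped. The plan then has no named comparison to report and no power for one, so any comparison made would be chosen after the fact. The statement of adequate power would also describe a property that the design does not have.

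**Working it through.** **Inputs.** From Sample Size and Power Calculations and Table 10: rates of 26% (metformin), 40% (combination) and 50% (OCP); 30% MetS at baseline; two-sided 0.05; 240 × 0.85 = 204 evaluable, 68 per arm.

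**1. Reproduce the stated power.** Cochran-Armitage test, scores s = 0, 1, 2, half-unit continuity correction:

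power = Φ[(T − 0.5 − 1.96√V0)/√V1]

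- T = Σ n·p·(s − s̄) = 68 × (0.50 − 0.26) = 16.32
- p̄ = (0.26 + 0.40 + 0.50)/3 = 0.3867; V0 = p̄(1 − p̄) × Σ n(s − s̄)² = 0.3867 × 0.6133 × 136 = 32.25, root 5.679
- V1 = 68 × (0.26 × 0.74 + 0.50 × 0.50) = 30.08, root 5.485
- (15.82 − 11.13)/5.485 = 0.855, so power is 80.4%

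| Table 10 row | Stated | 0/1/2 corrected | 0/1/2 uncorrected | 0/1/3 uncorrected |
|---|---|---|---|---|
| 25/38/50 | 84 | 84.0 | 86.1 | 84.1 |
| 25/38/52 | 89 | 89.2 | 90.8 | 89.7 |
| 26/40/50 | 80 | 80.4 | 82.8 | 79.6 |
| 26/40/52 | 86 | 86.4 | 88.3 | 86.2 |
| 28/42/52 | 80 | 79.7 | 82.1 | 78.9 |

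The sample size is right for the trend test. Equal spacing is the likely intent, but Table 10 does not prove it, since scores 0/1/3 also come within about one point of every row.

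**2. What the contrast compares.** Scores 0, 1, 2 centred on their mean give (-1, 0, +1), which is OCP versus metformin. Scores 0, 1, 3 give (-4, -1, +5), which compares the combination with neither agent singly. On the logit scale the (-1, 0, +1) Wald contrast has 81.2% power whether the combination rate is 10, 26, 40 or 60%. Trend-test power with the outer arms held at 26% and 50%:

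| Combination rate | 0/1/2 corrected | 0/1/3 uncorrected |
|---|---|---|
| 26% (equals metformin) | 81.9 | 89.6 |
| 40% | 80.4 | 79.6 |
| 50% (equals OCP) | 79.6 | 70.3 |

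Under either scoring, a significant trend is likely even if the combination is no better than OCP.

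**3. Unadjusted combination comparisons**, two proportions, 68 per arm. Power = Φ[(|difference| − 1.96·SE0)/SE1], with SE0 pooled and SE1 unpooled.

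- Versus OCP: (0.10 − 1.96 × 0.0853)/0.0849 = −0.79, power 21%. Expected odds ratio (0.40/0.60)/(0.50/0.50) = 0.67; standard error of its log √(1/27.2 + 1/40.8 + 1/34 + 1/34) = 0.347; 95% CI 0.34 to 1.31.
- Versus metformin: (0.14 − 1.96 × 0.0806)/0.0797 = −0.23, power 41%. Expected odds ratio 1.90 (0.92 to 3.93).
- Over the five Table 10 rows: 21–37% and 37–41%.
- Evaluable per arm for 80% power at 26/40/50%, n = [1.96√(2p̄(1 − p̄)) + 0.8416√(p1q1 + p2q2)]²/(p1 − p2)²: 388 versus OCP and 176 versus metformin.

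**4. Adjusted for baseline MetS, as planned.** This needs the baseline-to-6-month odds ratio, which the documents do not give. It is assumed to lie between 3 and 50. One guide is the earlier OCP trial: "The conversion rate to MetS was 28% in the OCP arm" over 16 weeks, denominator not stated. If that is among women free of MetS at baseline, 0.70 × 0.28 = 19.6% convert, and a 50% end rate would need 30.4 points from the 30 points of baseline cases. Persistence is therefore probably high. With a 50% end rate, persistence of 80, 90 and 95% gives odds ratios of 6.8, 18.4 and 42.9. For example, at 90% conversion is (0.50 − 0.27)/0.70 = 32.9%, and (0.9/0.1)/(0.329/0.671) = 18.4.

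Simulated logistic model: arm terms plus baseline MetS, balanced at 30%, one odds ratio in all arms, marginal rates held at 26/40/50%, 100,000 runs per setting. Site and race are not modelled because no figures are given.

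| Assumed odds ratio | Versus OCP | Versus metformin | OCP versus metformin |
|---|---|---|---|
| 1 | 21.2 | 41.6 | 82.8 |
| 3 | 22.5 | 43.0 | 85.4 |
| 10 | 25.9 | 51.0 | 91.3 |
| 20 | 28.7 | 57.9 | 94.8 |
| 50 | 32.8 | 68.1 | 97.9 |

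Over all Table 10 rows and odds ratios of 3 to 50, the ranges are 22–57% and 39–68%. From the information matrix of the same model, the expected odds ratio versus OCP is 0.65 (0.32 to 1.31) at 3 and 0.50 (0.20 to 1.23) at 50. Versus metformin it is 1.98 (0.93 to 4.19) and 3.82 (1.24 to 11.7). Evaluable per arm for 80% power falls to 367 and 170 at odds ratio 3, and to 232 and 98 at 50, all above 68.

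**The case against.** The strongest reply is that design, power and analysis agree with one another. The arms are ordered, the trend is the stated primary question, and linear trend conventionally means equal spacing. That stands: the primary test is sound, and the 0/1/3 scoring is only an illustration that appears nowhere in the plan.

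Second, the model already holds arm terms, so both odds ratios can be obtained from it. True, but none is named.

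Third, the longitudinal binary analysis might cover MetS: "For any binary outcomes collected at each visit, analyses will be based on generalized estimating equations (GEE) with a logit link". It names no pairwise contrast, and MetS needs laboratory values: "Blood will be collected at Screening, Randomization, week 16 and week 24 visits", so not at weeks 4 or 8. Repeated MetS could be derived at randomization, week 16 and week 24, but the text does not say so.

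Fourth, the power claim sits in background text and names no endpoint. That is fair. Still, the MetS trend is the only power calculation in the documents, so nothing else could support the claim.

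Fifth, the adjusted powers rest on an odds ratio that the documents do not supply. That also stands, and they should be read as a range. With strong persistence the comparison with metformin improves: its expected interval excludes 1 above an odds ratio of about 10. The comparison with OCP does not reach that point anywhere in the range.

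**Conclusion.** The concern holds. The plan is properly powered for a trend that, with equal spacing, is OCP versus metformin. It neither prespecifies nor powers a comparison of the combination with either single agent on MetS, so the statement of adequate power for single agent versus combination is unsupported. The unadjusted powers of 21% and 41% follow directly from the plan's own rates and 68 evaluable per arm. The adjusted ranges of 22–33% and 43–68% depend further on the assumed baseline odds ratio of 3 to 50, taken as common to all arms. No setting examined reaches 80%. This should be fixed, but it does not undermine the primary test.

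**What to change.** 1. Keep the trend contrast as the primary test and write out its coefficients. State that, with equal spacing, a significant result supports a difference between OCP and metformin and does not by itself place the combination.
2. Prespecify, from the same adjusted logistic model, the odds ratios with 95% confidence intervals for OCP+metformin versus OCP and OCP+metformin versus metformin. Label them as estimates rather than tests, reported whatever the primary result.
3. Reword the claim in Implications for the COMET-PCOS Trial: the 80% power belongs to the trend contrast, and the combination comparisons are not powered. If power is quoted for them, give the unadjusted 21% and 41% beside the adjusted ranges, with the assumed baseline odds ratios stated.
4. In the Synopsis hypothesis, name the comparator for the expected decrease with the combination. The planned 40% is below OCP (50%) but above the 30% baseline.

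Items 2 and 3 carry the weight; items 1 and 4 are clarifications. The cost is wording in the Synopsis (hypothesis and analysis), the Implications section and the Statistical Analysis section. No new model is fitted, and the primary test, its alpha, its power and the sample size do not change. The one drawback is that the stated power for the combination becomes less favourable.

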F-G Score: The Ferriman-Gallwey score is a measure for quantifying hirsutism in women. The Primary Investigator (or designee, which may be the subject) will assess each subject's hirsutism using the Ferriman-Gallwey scale at Screening, Randomization (if applicable and/or necessary) and 24 week visit. During the assessment for hirsutism, the PI (or designee) will also assess the subject's acne.

DXA: DXA scans will be completed on each patient at Randomization Visit and 24 week visit. The scanning will include a whole body scan, the lumbar spine and both hips.

Oral Glucose Test: OGTT will be performed at the randomization and at 24 week visit. Prior to the OGTT subject must fast overnight for minimum of 8 hours. If subject is not fasting, the blood work must be rescheduled. Patients will receive 75 g of an oral glucose solution at time zero (0) and blood will be sampled every 30 minutes for 2 hours for glucose, and insulin levels.

PCOSQ: The PCOSQ is a self-administered questionnaire for measuring health-related quality of life in women with PCOS. The PCOSQ will be administered to subjects at Randomization and 24 week visit.

STAI: The STAI (State-Trait Anxiety index) is a questionnaire for accessing trait anxiety and state anxiety. The STAI will be administered to subjects at Randomization and 24 week visit.

CES-D: The CES-D is a screening test for depressive symptoms. The CES-D will be administered to subjects at Randomization and 24 week visit.

FSDS-R: The FSDS-R (The Female Sexual Distress Scale-Revised) is a screening questionnaire for measuring sexually related personal distress in women with Female Sexual Dysfunction (FSD)

FSFI:The FSFI (Female Sexual Function Index) is a brief questionnaire measure of sexual function in women. ItCOMET-PCOS PROTOCOL V10.1NOVEMBER 30, 2021

was developed for the specific purpose of assessing domains of sexual function (e.g. sexual arousal, orgasm, satisfaction, pain) in clinical trials.

ASA24: The Automated Self-Administered 24-Hour Dietary Assessment Tool (ASA24). This 24-hour dietary recall captures detailed information about all foods, drinks, and supplements (including vitamins, minerals, herbals, and other dietary supplements) you consumed from midnight to midnight. You will be asked to complete this at 12 weeks and 24 weeks.

Concomitant Interventions

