- 1. Both MetS and PCOS are major health problems and the risks of common treatments (OCP or metformin) on development of MetS are poorly understood.
- 2. Knowledge gained from this investigation will identify optimal strategies for treatment of overweight/obese women with PCOS
- 3. Understanding the underlying pathophysiology for alterations in metabolic risk with OCP or metformin use, will provide important information for future studies.

Statistical Considerations

General Design Issues

This will be a randomized, double-blind, double dummy clinical trial of three types of medication, OCP + placebo, metformin + placebo or OCP + metformin. We will track all subjects to completion. Subjects will be randomized 1:1:1 to the three treatments.

Randomization

Randomization is a critical feature of a clinical trial because it prevents treatment-selection biases. The study statistician will develop the programs for the randomization; however, the final random seeds used to generate the randomization scheme will be prepared by a statistician in PSU's Department of Public Health Sciences independent of the study in order to keep the study statistician blinded as well. The randomization scheme for this study will use variable-size, random permuted blocks to ensure that the number of participants in each treatment arm is balanced after each set of *B* randomized participants, where *B* is the block size. Furthermore, the randomization will be stratified by recruitment site (UPenn/PSU), race (AA/non-AA), and the presence of MetS at baseline (yes/no). Randomization to the metformin or OCP arms will use 1:1:1 allocation.

Outcomes

Primary Outcome Measurements

The primary outcome for this trial is prevalence of MetS.

Secondary Outcome Measurements

We may assess change in HDL-C function, serum apolipoproteins, lipid particle size and number, body fat distribution, BMI, serum adipokines, HbA1c, glucose and insulin sensitivity, serum markers of inflammation, free fatty acids, androgens, quality of life parameters, cognitive testing and predictive factors for change in prevalence on MetS

Sample Size and Accruals

Sample Size and Power Calculations

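### The mixed model for the continuous secondary outcomes does not adjust for the outcome's own baseline value, so its change contrasts are valid but less precise than the collected data allow

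*Combined protocol and SAP*

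**What the plan says.** Under Statistical Considerations, Statistical Analysis, the model for the continuous secondary outcomes is: "The independent variables in the model will be treatment arm, time, the interaction of treatment and time, and the 3 randomization stratification factors". The Synopsis lists the same terms. The hypothesis tests follow from it: "From the mixed-effects models, contrasts will be constructed to test the hypotheses of interest with respect to changes over time in the outcomes".

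The stratification factors are site, race (AA or not) and MetS at baseline (yes or no). The section says "All analyses will include these 3 randomization stratification factors as covariates in the statistical models", but none of the three is the baseline value of a continuous outcome. After the first fit, "we will add covariates to the models that correspond to other potential confounders (e.g., age) to assess their impact"; age is the only example named. Nowhere is the outcome's baseline value added as a predictor, or a common baseline mean imposed. The section does not say whether the randomization value is a response or is subtracted beforehand, whether time is categorical or linear, or which covariance structure is used.

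Several of these outcomes have one baseline and one scheduled follow-up measurement: "DXA scans will be completed on each patient at Randomization Visit and 24 week visit" and "OGTT will be performed at the randomization and at 24 week visit". The PCOSQ follows the same two-visit pattern. Fasting bloods are scheduled at randomization, week 16 (headed as optional in 7.2.7) and week 24.

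**The concern.** With an arm main effect and an arm-by-time term, each arm has its own free mean at randomization. The change contrast is then the difference between arms at follow-up minus the whole difference at baseline. Randomization makes the true baseline difference zero, so any observed difference is chance. The efficient correction subtracts only the part that predicts follow-up, which is about rho times the difference when the SDs are equal. Subtracting all of it adds noise. A mixed model does not avoid this, because the free baseline means remain in it.

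At stake is the width of the intervals for cholesterol efflux, apolipoproteins, lipid particles, body fat, adipokines, androgens and quality of life. The sample size was set for MetS prevalence alone, so precision for these outcomes depends on the model chosen.

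**Working it through.** **Plan's own figures.** The only sample-size figure concerns the primary outcome: 204/0.85 = 240, which reproduces. A trend test at 68 per arm with 26%, 40% and 50% has 80.4% power with a continuity correction, against 80% stated. No SD, correlation or power is given for the secondary outcomes, so no stated figure is disputed.

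**Inputs.** 80 per arm; "We anticipate a 15% subject drop-out over the course of the trial", so m = 68 of n = 80 have week-24 data; drop-outs' baselines stay in the mixed model, as the plan says. Assumed: equal SD s at both times, correlation rho, missing completely at random.

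**Variance per arm, two visits**
- Planned change estimate: s²[(1-rho²)/m + (1-rho)²/n]
- Baseline-adjusted estimate: s²(1-rho²)/m
- Ratio of interval widths: √[1 + (m/n)(1-rho)/(1+rho)], with m/n = 0.85
- Complete data: √[2/(1+rho)]

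Example, rho 0.3: 0.85 × 0.7/1.3 = 0.458; √1.458 = 1.207.

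| rho | Planned width / adjusted width, 15% drop-out | No drop-out | Extra variance at 15% |
|---|---|---|---|
| 0.3 | 1.207 | 1.240 | 46% |
| 0.5 | 1.133 | 1.155 | 28% |
| 0.7 | 1.072 | 1.085 | 15% |
| 0.9 | 1.022 | 1.026 | 4% |

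A simulation of 20,000 two-arm comparisons gave 1.210 at rho 0.3 and 1.021 at rho 0.9, with both estimators centred on zero under no effect.

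**Other readings of the model**
- *Categorical time, third visit at week 16, equal correlations, 15% drop-out:* 1.208, 1.134, 1.073 and 1.023.
- *Change at week 24 as the response, completers only:* intervals about 23%, 15%, 8% and 2% wider than with baseline added.
- *Linear time, weeks 0, 16 and 24, complete data:* the mean time is 13.33 and the sum of squares 298.67. With a random intercept the 24-week contrast gives baseline weight 24 × 13.33/298.67 = 1.07. The loss is 33%, 20%, 11% and 3%.
- *Linear time, weeks 0, 4, 8, 16 and 24 (weight, waist):* 24 × 10.4/371.2 = 0.67. The loss for this schedule was not computed.

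**What the documents suggest about rho.** Take the SD of change from the Table 5 intervals (t-based, n = 34 OCP, n = 98 metformin) and the baseline SD from Table 4, a different PCOS sample. Then rho = 1 - SDchange²/(2 × SDbaseline²).
- HDL-C, SD 16.1: SDchange 10.0 and 11.7, so rho 0.81 and 0.74; intervals 4.5% and 6.3% wider (3-9% allowing for sampling error in SDchange).
- Small LDL, SD 367.95: SDchange 220.7 and 257.6, so rho 0.82 and 0.75; intervals 4.1% and 5.8% wider (3-8%).
- Efflux: the same method points to a lower rho and a larger loss, but no figure is given. The Table 4 spread is an unlabelled range, the printed interval for the difference does not contain that difference, and sampling error in SDchange alone leaves rho anywhere from 0.02 to 0.63.
- LDL-C and large VLDL are not used. Mean LDL-C plus HDL-C (167.1 + 54.7 = 221.8) exceeds total cholesterol (192.5), and large VLDL cannot be on one scale in both tables (4.04 against a change of 206.2).

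**The case against.** The planned model is a common choice and gives valid tests. The outcomes carry no power claim, and the protocol is tentative about them: "We may assess change in HDL-C function, serum apolipoproteins, lipid particle size and number". No rho is given, so the 2-21% range is a formula evaluated at assumed values. Where the documents' figures can be used with least strain the loss is 4-6%, and HDL-C level is not itself a listed secondary outcome. The model is also underspecified, so a baseline weight of exactly 1 cannot be asserted throughout.

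Most of this stands. The analysis is valid, the range is illustrative, and weight 1 is conditional on categorical time or change as the response. What does not follow is that the vagueness removes the point. Outcomes with two visits leave no choice of time coding, and with linear time over weeks 0, 16 and 24 a loss remains.

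A reader might go further and infer that the stratification factors and the later age adjustment do nothing, because effects constant over time cancel from a change contrast. The documents do not support that as a separate criticism. It depends on the randomization value being a response, which is not stated, and letting the factors act on post-baseline values changed the variance by only about 0-2% in simulation.

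**Conclusion.** The point holds as a loss of precision on continuous secondary outcomes. At 15% drop-out the planned intervals are about 21%, 13%, 7% and 2% wider than needed at rho 0.3, 0.5, 0.7 and 0.9, assuming equal SDs and data missing completely at random. HDL-C and small LDL fall near 4-6% on a reading that mixes two samples. Efflux may lose more, but by an amount the documents cannot fix. The other outcomes were not computed.

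Weight 1 applies exactly to complete two-visit data, and to other outcomes if time is categorical or change is the response; with drop-out it applies closely.

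Two stronger readings should be resisted. One is that the comparisons are biased: randomization centres both estimators on the true effect. The other is that the trial's 80% power suffers: that figure belongs to the logistic analysis of MetS, which this does not touch. This is a worthwhile free improvement, not the repair of an invalid analysis.

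**What to change.** For the continuous secondary outcomes, specify one of these before unblinding:
- a mixed model with the randomization value as a response, a common mean across arms at that visit, categorical time, arm-by-post-baseline-time terms and unstructured within-subject covariance; or
- a model for post-baseline values with the outcome's baseline value as a covariate.

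State the response, time coding and covariance structure. Leave the GEE for binary outcomes and the primary logistic model as written.

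The cost is a paragraph of SAP text and the model code. No new data are needed. The estimand, the difference between arms in mean change, stays the same because baseline is measured before treatment in randomized arms.
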